#### *17.4.4 Exploratory analyses*

In an exploratory analysis, we will correlate Mediterranean Diet score with patient-reported fatigue using the FACIT-F fatigue score at 4 weeks and 8 weeks. We expect that the majority of participants will improve their Mediterranean Diet score, and that 4 and 8 week scores will range from 5-14 in the intervention group (higher is better). We expect that the fatigue subscale of the FACIT-F will range from 0-43 out of 52 based on a historical dataset (Kleckner et al.; a higher score indicates less) and that FACIT-F total scores will range from 44-160 out of 160^161 (higher is better well-being). We will also assess correlations between baseline Mediterranean Diet score (proxy for improvement in diet quality) and change in fatigue to evaluate the influence on baseline diet on the development of fatigue. Further, we will assess the change in the Mediterranean Diet score and the change in fatigue to see if a greater shift in diet led to a greater prevention of fatigue.

Other measures collected via patient-reported outcome questionnaires (e.g., BFI, Fact-Cog) will be analyzed using similar methodology as outlined in the Aim 2 (FACIT-F score analysis).

**Because of the small sample size in this study and the resulting low statistical power, these secondary and exploratory analyses will be interpreted very cautiously and only used to aid in the designing of a study for our larger trial and generation of new hypotheses.**

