### *2.1.4 Nutrition as a behavioral intervention*

The National Academy of Sciences emphasizes the importance of expanding cancer treatment to include promotion of a healthy lifestyle, including a healthy diet, weight management, and physical activity. There have been many cross-sectional studies demonstrating that "higher quality" dietary patterns are associated with fewer symptoms during and after cancer treatment, as well as a reduced risk for recurrence and mortality. The definition of "higher quality" varies, but usually refers to dietary patterns that are rich in fruits, vegetables, whole grains, unprocessed lean meat products (e.g., chicken breast, seafood) or lean protein sources, and low in added sugar and highly processed carbohydrates. Moreover, patients with cancer intuitively understand the importance of nutrition: at least 70% of patients

take supplements to improve their nutritional status, a percentage that is much higher than individuals without cancer. Some of these supplements are indeed beneficial, but many are inert and some are dangerous. A 2018 systematic review and meta-analysis concluded with recommendations for high antioxidant intake from fruits and vegetables but *not* antioxidant supplements to prevent chronic diseases such as cancer, which was corroborated in a 2020 study showing that antioxidant supplements increased the hazard of cancer recurrence. Also, unfortunately, results of supplement studies are also often inconsistent, so that guidelines for cancer survivors are not clear. For example, in a recent review (Inglis et al.), we evaluated nutritional interventions for cancer-related fatigue and found that previous research on supplements for treating cancer-related fatigue such as ginseng and guaraná led to inconsistent findings.

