dose delays or changes to the chemotherapy schedule, we will still collect assessments at the originally planned time.) We estimate attrition between approximately 20 and 25%, thus we estimate to retain 33 (22:11) evaluable patients. This sample size is appropriate for small randomized pilot studies and it will allow us to obtain preliminary estimates of descriptive statistics [mean, standard deviation (SD), and confidence intervals (CI)]. The primary endpoint is the change in fatigue as measured by FACIT-F from baseline (T1) to 4 weeks (T2). Assuming a correlation of 0.50 between T1 and T2 FACIT-F measurements, a total sample size of n=33 will provide 80% power at the 0.15 two-sided significance level to detect an effect size (ES, standardized mean between-group difference) of 0.75 of the intervention effect on change in T2-T1 FACIT-F using analysis of covariance (ANCOVA) with T1 FACIT-F as a covariate (**Fig. 3**). The estimates of T1-T2 correlation and attrition rate are based on our prior studies.

Feasibility is often determined for nutrition interventions among 10-15 participants (e.g.,); pilot preliminary efficacy studies usually recruit 20-30 (e.g.,). **Table 6** below shows prior studies that are similar to this one, including their sample size.

Study	n	Population	Intervention	Outcome	Results
Zick et al. (2017) 	30	breast cancer survivors	Fatigue reduction diet vs. General Health Curriculum (time and attention control) for 3 months	Brief Fatigue Inventory	From baseline to 3-months, fatigue improved by 44±39% in diet group compared to 8±34% in the control group (p=0.01)
Skouroliakou et al. (2018) 	70	breast cancer survivors	Mediterranean Diet for 6 months vs. handout	serum antioxidant capacity and body composition	The dietary intervention based on Mediterranean Diet improved serum antioxidant capacity, body composition, and glycemic profile.
McMillan et al. (2011) 	27	healthy women in their 20's	Mediterranean Diet vs. control for 10 days	Profile of Mood States	A group × time interaction demonstrated that the Mediterranean Diet reduced fatigue (p=0.16) and improved vigor (p<0.01).

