### *17.2 Data Handling, Rigor, Quality, and Reproducibility:*

Data will be entered in REDCap electronic forms and electronically collated in a HIPAA-compliant REDCap database managed by our Division. After collation, data will be audited electronically and visually, as needed, for errors. Appropriate graphical or statistical diagnostics methods will be employed in each of the analyses to evaluate distribution of variables (e.g., to identify shape of the distribution and outliers) and also to evaluate the model assumptions (e.g., if deviation from the statistical assumptions is found, we will use alternative methods such as transformations or nonparametric analyses). Outliers that are detected will be investigated to determine if they are due to error. If not, analyses will be conducted with and without them to assess sensitivity. Because this is a preliminary efficacy study, unless stated otherwise, all hypothesis testing will be at the two-sided 0.15 level as appropriate for screening trials. SAS, JMP, and/or R software will be used for the analyses. Following the intent-to-treat principle, all randomized survivors will be analyzed in the arm as allocated, regardless of their compliance with the intervention or Mediterranean Diet contamination in the control group.

Although participants will be randomly assigned, differences may be present between study arms on demographic or clinical variables. Study arms will be compared on baseline demographic (e.g., age), clinical (e.g., cancer diagnosis, type of chemotherapy), and behavioral (e.g., physical activity, smoking) variables. If significant imbalance is found for a variable, it will be included as a covariate in subsequent analyses following standard practice.

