#### *17.4.2 Aim 2: Patient-reported fatigue*

To provide estimates of efficacy comparing the Mediterranean Diet to usual care for alleviating fatigue, we will evaluate between-arm difference in mean change in FACIT-F fatigue subscale score from baseline to 4 weeks in an ANCOVA model. The outcome will be FACIT-F fatigue score at 4 weeks with arm included as a fixed effect and FACIT-F fatigue score at baseline as a covariate. To assess the moderating effect of the baseline level of fatigue we will test arm×baseline interaction. To further evaluate the longitudinal trajectory of fatigue and the maintaining effect of the intervention, we will incorporate FACIT-F fatigue score measured at all time points (T1, T2, T3) in a repeated measures linear mixed model. The impact of patient's variables (e.g., age, gender, body mass index) on the results will be assessed by adding the covariates to the models. The results of the analyses together with the estimates of distribution parameters (e.g., mean, SD) of T1-T3 FACIT-F fatigue score values as well as the change scores will be used in planning a future randomized trial.

We expect all measures of cancer-related fatigue to increase over the course of chemotherapy, though we hypothesize that the differences will be attenuated in the intervention group. We will also compare our baseline-to-post-intervention change scores to those obtained via historical controls (e.g., [name] et al., 2018).

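### Section 17.4.4: the correlation of baseline diet score with change in fatigue carries two meanings of opposite sign, names no arm or baseline-fatigue term, and leaves its estimand unstated

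*Combined protocol and SAP*

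**What the plan says.** The sentence at issue is in section 17.4.4 (Exploratory analyses): "We will also assess correlations between baseline Mediterranean Diet score (proxy for improvement in diet quality) and change in fatigue". Its purpose follows directly: "to evaluate the influence on baseline diet on the development of fatigue". No arm term, baseline FACIT-F term, time point or type of coefficient is given.

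No other section supplies them. The sentence in 17.4.4 that carries the Aim 2 methods over concerns other questionnaires, such as the BFI. Section 4.4.4 promises adjustment for factors associated with fatigue and gives depression as an example, but does not name baseline fatigue. By contrast, the Aim 2 model in 17.4.2 has arm as a fixed effect and "FACIT-F fatigue score at baseline as a covariate". The biomarker ANCOVA models in 17.4.3 also adjust for baseline values.

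Section 17.2 sets the default level: "all hypothesis testing will be at the two-sided 0.15 level as appropriate for screening trials". Section 17.4.4 closes by asking for very cautious interpretation because of small numbers and low power, and limits use to designing the larger trial and generating hypotheses.

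**The concern.** There are two separate problems.

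**Two meanings for one number.** A higher FACIT-F score means less fatigue. If a good baseline diet protects, baseline diet score should correlate positively with FACIT-F change. If a low baseline score stands for room to improve, and improving helps, the correlation should be negative. The second reading needs an intervention that moves the score. It fits the diet arm, where patients scoring 10 or more are excluded at entry (section 5) and full adherence to the provided food gives 13 of 14 points (17.4.1). It has no basis in usual care, where no specific dietary advice is given (4.3.2). If the arms are pooled, the two effects can cancel.

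**Change score without baseline fatigue.** Baseline diet is not randomised, so nothing in the design makes it independent of baseline fatigue. Section 2.1.4 says that better "dietary patterns are associated with fewer symptoms during and after cancer treatment". Both instruments also look back over the same past week (4.4.1, 4.4.2). A correlation with change then tests something other than influence given where the patient started.

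At stake is a coefficient that could be misread when the larger trial is designed. The caution in 17.4.4 is about low power, not about mixed meaning or a shifted null.

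**Working it through.** **Inputs from the plan.** Section 17.1 assumes a correlation "of 0.50 between T1 and T2 FACIT-F measurements, a total sample size of n=33 will provide 80% power at the 0.15 two-sided significance level" and aims "to detect an effect size (ES, standardized mean between-group difference) of 0.75 of the intervention effect". The expected evaluable split is 22:11. **Assumed:** rho, the correlation of baseline diet score with baseline FACIT-F, taken over 0 to 0.4 because the documents give no figure. Positive rho means that better diet goes with less fatigue.

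**1. The plan's own figure.** For ANCOVA the residual SD is sqrt(1 - 0.5²) = 0.866. The standard error is 0.866 × sqrt(1/11 + 1/22) = 0.320, and 0.75/0.320 = 2.35. Two-sided 0.15 has critical value 1.44, so power is Φ(2.35 - 1.44), about 82%. With the t distribution on 30 degrees of freedom it is 80.6%. The stated 80% reproduces with baseline adjustment. With an unadjusted change score it would be about 71%.

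**2. Pooling.** Suppose, for illustration, a slope of +0.3 in usual care and -0.15 in the diet arm. The pooled slope is (11 × 0.3 + 22 × (-0.15))/33 = 0. Simulated rejection is about 16% against a nominal 15%, so two real and opposite relations look like nothing. This needs no assumption about rho.

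**3. Expected correlation with no influence given starting fatigue.** Let D be baseline diet, and F1 and F2 be FACIT-F at T1 and T2, all standardised. If D relates to F2 only through F1:
- cov(D, F2 - F1) = 0.5 × rho - rho = -0.5 × rho
- var(F2 - F1) = 2 × (1 - 0.5) = 1
- so corr(D, F2 - F1) = -0.5 × rho.

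Simulated rejection in this model, n = 33, two-sided 0.15:

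| rho | correlation with change | adjusted for F1 |
|---|---|---|
| 0 | 15.0% | 15.0% |
| 0.1 | 16.8% | 15.0% |
| 0.2 | 21.0% | 15.2% |
| 0.3 | 28.6% | 15.2% |
| 0.4 | 38.2% | 15.2% |

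At rho = 0.3, a T1-T2 correlation of 0.3 or 0.7 in place of 0.5 gives about 34% or 23%.

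**4. A real protective influence.** Take b = 0.3 SD of FACIT-F per SD of diet score at fixed baseline fatigue. The covariance with change is b × (1 - rho²) - 0.5 × rho. At rho = 0.3 that is 0.273 - 0.150 = 0.123, so over half of the signal is offset. Power:

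| rho | correlation with change | adjusted for F1 |
|---|---|---|
| 0 | 61% | 71% |
| 0.2 | 36% | 69% |
| 0.3 | 24% | 68% |
| 0.4 | 17% | 64% |

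The adjusted column is a test on all 33 patients.

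**5. The counter-model.** Let D relate only to a stable fatigue level that underlies both F1 and F2, with no effect on change. The covariance with F2 - F1 is then zero, and the planned correlation rejects in about 15% at every rho. The adjusted test now rejects in 23%, 34% and 49% at rho 0.2, 0.3 and 0.4.

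**The case against.** The strongest reply is that the right null is a matter of choice. Step 5 is Lord's paradox: which analysis is off-centre depends on how diet and fatigue are related, and the plan does not say. For a question about how fatigue develops, change is a defensible target. Nor does Aim 2 settle it. Arm is randomised there, so baseline adjustment is safe; baseline diet is not randomised. This stands, and it is why the point is that the estimand must be stated, not that one test is wrong.

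The size also depends on an unknown rho. Section 2.1.4 speaks of symptoms during and after treatment, whereas baseline is ideally taken before the first infusion (8.2.7). Excluding scores of 10 or more narrows the diet range and may lower rho. At rho = 0.1 the excess is under 2 points. This stands too.

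The text is silent rather than explicit. That the change is unadjusted and the arms are pooled is the natural reading, but it is not stated. Silence does not remove the two-meanings problem, because the proxy wording is in the sentence itself.

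A reader might also expect the power gain in step 4 to carry over to a slope estimated in usual care alone. It does not. With 11 patients, that slope from an interaction model has about 36 to 38% power for the same effect, and under the counter-model it too over-rejects (17 to 28% at rho 0.2 to 0.4).

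**Conclusion.** The point holds as a minor one. As worded, the coefficient has two readings of opposite sign, and pooled over arms it supports neither. That part needs no figure from outside the documents.

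The second part is conditional. If rho is not zero and the question is influence given starting fatigue, the planned test is centred on -0.5 × rho. It rejects falsely in about 17 to 38% of trials for rho 0.1 to 0.4, and with rho positive it masks a protective influence. A harmful influence would be exaggerated instead, and a negative rho reverses the directions.

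A reader might infer that regression to the mean always biases this analysis, or that baseline adjustment is always the valid test. The documents support neither: they give no rho and no causal model, and step 5 reverses the ranking. A reader might also infer that a spurious result would be taken as support for the trial's hypothesis. That is speculation, given the explicit caution in 17.4.4. Aim 1, Aim 2 and the sample size are unaffected.

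**What to change.** Change the wording of 17.4.4:

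1. State the estimand: influence of baseline diet on later fatigue given starting fatigue, or association with change.
2. Regress FACIT-F fatigue score at 4 weeks, and at 8 weeks, on baseline FACIT-F fatigue score, arm and baseline diet score. Under the model of steps 3 and 4, this pooled slope has about 64 to 70% power for a 0.3 SD effect at rho 0.2 to 0.4, against about 17 to 36% for the planned correlation.
3. Add an arm by baseline diet term and report the arm-specific slopes as descriptive only.
4. Report the observed correlation of baseline diet score with baseline FACIT-F, so that readers can judge how far the two analyses should differ.
5. Keep the change-score correlation as a sensitivity analysis, and comment where the two disagree.
6. Limit the proxy-for-improvement reading to the diet arm. The same section already plans to relate change in diet score directly to change in fatigue.

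No new data are needed. The cost is a few model degrees of freedom out of about 33 patients, and an imprecise usual-care slope (11 patients, about 37% power).
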